4.2 Risk/Benefit Assessment

Enoxaparin and apixaban are both FDA approved in the context of VTE prophylaxis and prescribed after cystectomy as standard of care (SOC). The benefits of postoperative anticoagulation for reducing rates of VTE have been repeatedly demonstrated in the literature and are included in society guidelines (see Section 2.1). The most relevant clinical risk with either medication is bleeding, which is a low risk at the prophylactic dose utilized in this study.

The most important point in assessing risk/benefit in this study is that the standard of care includes extended prophylaxis (EP) postoperatively. Thus, participants will neither gain clinical benefit nor avoid clinical risk by participating because they would have been given EP regardless. The selection of one of these two anticoagulants is currently determined by

prescriber preference in clinical practice. Enoxaparin is currently the more commonly prescribed at this institution so is considered the "control" group for notation purposes in this trial.

5 STUDY POPULATION

5.1 Inclusion Criteria

In order to be eligible to participate in this study, an individual must meet all of the following criteria:

- 1. Provision of signed and dated informed consent form
- 2. Stated willingness to comply with all study procedures and availability for the duration of the study
- 3. Able to communicate in English over the phone
- 4. Male or female, age >18 years
- 5. Diagnosed with biopsy-proven, urothelial cell carcinoma (any T stage, N0-1, M0) with plan for radical cystectomy with urinary diversion and concurrent pelvic lymph node dissection as treatment

5.2 Exclusion Criteria

An individual who meets any of the following criteria will be excluded from participation in this study:

- 1. Preoperative use of a therapeutic dose of anticoagulant (this notably does *not* exclude patients taking antiplatelet agents)
- 2. Failure to undergo radical cystectomy with concurrent urinary diversion and pelvic lymph node dissection
- 3. Failure to be discharged by POD14
- 4. Failure to receive a script for enoxaparin or apixaban.
- 5. Any medical condition which precludes treatment with *either* enoxaparin *or* apixaban (including dialysis, hemophilia or any other bleeding diathesis)

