- National Institute of Health (NIH) Patient-Reported Outcomes
 Measurement Information System (PROMIS) Medication
 Adherence Scale (PMAS) a validated, nine-item, patient-reported
 measure of medication adherence¹
- 2. Patient Satisfaction a series of independent questions that investigate barriers to adherence specific to apixaban or enoxaparin

To address our secondary objective of comparing cost, secondary endpoints also include:

- 3. Patient out of pocket cost for anticoagulant prescription (in dollars)
- 4. COST-FACIT, a 12-item survey developed and validated in the cancer population for assessing patient-reported financial distress due to healthcare costs²

Study Population:

Inclusion Criteria: All patients undergoing RC with urinary diversion and pelvic lymph node dissection for urothelial bladder cancer (any T stage, N0-1, M0) at the participating institutions.

Exclusion Criteria:

- 1. Preoperative use of a therapeutic dose of anticoagulant (this notably does *not* exclude patients taking antiplatelet agents)
- 2. Failure to undergo radical cystectomy with concurrent urinary diversion and pelvic lymph node dissection
- 3. Failure to be discharged by POD14
- 4. Failure to be discharged on prophylactic enoxaparin or apixaban.
- 5. Any medical condition which precludes treatment with *either* enoxaparin *or* apixaban (including dialysis,hemophilia, or any other bleeding diathesis)
- 6. Inability to communicate over the phone in English

Due to the natural history of bladder cancer, the expected population will be mixed in age, race, gender, and general health status, though likely to be majority white males between the ages of 50-80 in generally good health status (enough that they are safe to undergo RC, which is a major surgery).

Target sample size is 108 participants

Enrolling Sites: Hospital of the University of Pennsylvania (HUP), Philadelphia, PA

Vanderbilt University Medical Center, Nashville, TN

Description of Study Intervention:

Enoxaparin and apixaban are both established treatments in clinical practice and considered acceptable standards of care. However, enoxaparin has historically been utilized for extended prophylaxis prior to the availability of apixaban and is slightly more commonly prescribed. Hence, in this study, randomization to apixaban will be considered the intervention for convention.

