1.2 Schema

Screening participants by inclusion and exclusion criteria **Pre-operative** Obtaining informed consent, Enrolling participants **Clinic Visit Demographics Questionnaire** Surgery, Inpatient Recovery Randomization Apixaban Enoxaparin Discharge At home, self-administration of anticoagulant Phone Call #1: • Medication counting **POD 30** PROMIS, Patient Satisfaction Questionnaire (end of Chart review for perioperative variables & pharmacy prophylactic cost data anticoagulation) Screening for VTE & bleeding Phone Call #2: **POD 90** • COST Questionnaire Screening for VTE & bleeding

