4.1 Minimizing Bias

Patients will be randomized to a prescription for one of the two anticoagulants at the time of postoperative discharge, and instructed to continue the medication until POD30. Randomization will be performed in a simple 1:1 fashion.

The randomization will be non-blinded. Given that this trial aims to explore the real experience of patients on these medications, blinding and placebo would actually detract from the important clinical context and understanding that participants have. Furthermore, enoxaparin and apixaban have different routes of administration (enoxaparin is injectable and apixaban is oral) which makes blinding and placebo infeasible. Blinding of the investigators is not necessary given the outcomes are patient reported surveys and pill/vial counts. Bias will be sufficiently reduced by randomization.

The University of Pennsylvania will serve as the primary site, and Vanderbilt University Medical Center as a second site. The addition of a second site will also introduce variety into the study population and strengthen its applicability.

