8.2 Discontinuation of Study Intervention, Discontinuation from Study

Prophylactic anticoagulation is standard of care after RC and therefore the decision to stop prophylaxis should be situated within a discussion with the treating clinician. The following are anticipated reasons participants may be told to discontinue study intervention (ie stop their anticoagulant) by their treating clinician:

- Development of blood clot. This would require discontinuation of prophylactic dose in favor of therapeutic dose and may involve switching anticoagulant type
- Development of bleeding event
- Development of an adverse event possibly related to the anticoagulant

- Development of a serious adverse event that would make prophylactic anticoagulation contraindicated

If study personnel discover any of these occurrences during study visits and they are not known already to the treating clinician, study personnel will refer the participant to their treating clinician for management, which may include consideration of discontinuation of the anticoagulant.

Study personnel will screen for discontinuation of the study intervention (ie discontinuation of the assigned anticoagulant) that has already occurred at the beginning of the POD30 and POD90 telephone calls. Any instances of study discontinuation will be brought to the attention of the PI and at the discretion of the PI participants who must discontinue the study intervention may remain in the study and complete portions of study visits depending on their reason for anticoagulant discontinuation and length of time they were following study protocol.

Participants may alternatively be discontinued completely from the study for the following reasons:

- Failure to undergo radical cystectomy and pelvic lymph node dissection
- Failure to be discharged on prophylactic anticoagulant
- Failure to be discharged by POD14
- Lost to Follow Up, defined as failing to complete the study visit despite three attempts to contact the participant via phone and/or email
- Participant request; participants are free to withdraw at any time

Any study discontinuation or discontinuation of the study intervention will be documented, including the date and reason for discontinuation. All instances will be reviewed by PI.. Participants who are discontinued will not be replaced.

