8.3 Crossover Between Study Arms

If a participant has or develops a contraindication to the specific drug they have been randomized to receive prior to discharge on EP (ie prior to initiation of the study intervention), they will be considered for crossover to the other arm and, if there is no contraindication to the other drug, can be switched to that arm. These instances and reasons for crossover will be documented. Crossover in this way will be allowed so that patients are not deprived of the standard of care anticoagulation after RC for their participation in the study and to better mimic the current prescribing patterns in which the drugs are frequently substituted for each other. Potential bias from allowing crossover is expected to be minimal as there is not a strongly plausible link between the contraindications to enoxaparin or apixaban and adherence to enoxaparin or apixaban. Furthermore, the contraindications to enoxaparin and apixaban are mostly quite rare; the only anticipated contraindication will be creatinine clearance (CrCl) <30 for enoxaparin. Any other possible indication for crossover will be reviewed by PI. Patients who crossover should still complete the study visits and both an intention to treat (ITT) and perprotocol (PP) analyses will be completed.

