9.7 Populations for Analyses

The analysis of primary endpoint, PDC, as well as analyses comparing the results of the questionnaires will be conducted using an Intention-to-Treat (ITT) Dataset consisting of all randomized participants. We expect minimal crossover after randomization however if there is significant crossover we would also perform the analysis in an "As Treated" (AT) dataset consisting of participants categorized to the drug they ultimately received after crossover. Cost analyses will be performed using a dataset of all prescriptions (there may be more than one prescription per participant if there is crossover between study arms, though again this is expected to be minimal). Safety analyses will be performed in the ITT dataset as well as in participants who meet criteria for "adherent" to their anticoagulant (as defined above in section 9.4). Missing data will be assumed random and discarded from all analyses; missing data is expected to be low as there are only two study visits.

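### Randomised participants who never obtain the drug can be dropped from the ITT analysis or, if their script goes unfilled, scored as fully adherent; a bias toward non-inferiority is plausible but not shown

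*Combined protocol and SAP*

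**What the plan says.** **Timing of allocation.** Section 4.1: "Patients will be randomized to a prescription for one of the two anticoagulants at the time of postoperative discharge". The schema in section 1.2 has the order "Surgery, Inpatient Recovery Randomization Apixaban Enoxaparin Discharge". Section 8.3 provides for a participant with a "contraindication to the specific drug they have been randomized to receive prior to discharge on EP", so the plan itself expects events between allocation and discharge.

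**Exclusion and discontinuation.** Section 5.2, item 4: "Failure to receive a script for enoxaparin or apixaban". The synopsis (section 1.1) words the same item as "Failure to be discharged on prophylactic enoxaparin or apixaban". Section 8.2 gives "Failure to be discharged on prophylactic anticoagulant" among the reasons for which a participant may be taken out of the study altogether, and adds: "Participants who are discontinued will not be replaced".

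**Analysis set.** Section 9.7 analyses PDC in an "Intention-to-Treat (ITT) Dataset consisting of all randomized participants". The same section treats missing data as random and leaves them out of every analysis.

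**Unfilled scripts.** Under section 6 the participant fills the prescription and pays for it. Someone who has the prescription but complies poorly counts as having received the intervention, and that poor compliance is the primary outcome. Sections 7.1 and 9.3 obtain the amount taken by subtracting the units left at the POD 30 call from the size of the prescription, which is read from the medical record.

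**The concern.** The script for the allocated drug comes with or after allocation. An exclusion that depends on the script, or on leaving hospital with the drug, can therefore act on people who are already randomised. Sections 5.2 and 8.2 would then take out participants whom section 9.7 says are analysed, and no rule gives them a PDC.

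The wording also differs. The synopsis and section 8.2 turn on being discharged on the drug; sections 5.2 and 6 turn on the script. A participant with a script and a refused authorisation could be out under one wording and in under the other.

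Staying in does not solve the problem. A participant who never fills the script has no units left, so the subtraction returns the whole prescription as taken. Failing to obtain the drug is non-adherence, yet the formula gives it the best possible score.

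The primary comparison is at stake. If more apixaban than enoxaparin participants fail to obtain the drug, either route raises the apixaban mean relative to enoxaparin and eases the non-inferiority conclusion. The protocol's own hypothesis (section 1.1, objective 3) is that apixaban barriers come mainly from insurance coverage and cost, which makes it hard to treat these losses as random.

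**Working it through.** **1. The plan's figure.** Section 9.3.1 gives control PDC 85%, margin 15 points, one-sided 0.05, 80% power and 45 per arm. With PDC treated as continuous and no true difference, n = 2(1.645 + 0.842)² SD² / 0.15². This gives 45 when SD is about 0.286. Treating 85% as a binomial proportion in both arms gives (1.645 + 0.842)² × 2 × 0.85 × 0.15 / 0.15², or 71 per arm. That mismatch is a separate matter. Here it serves only to choose an SD consistent with 45. The documents state no SD; 0.25 to 0.286 is an assumed range.

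**2. Evidence on arm dependence.** Table 2 (section 2.3): prior authorisations denied were 9/41 = 22.0% for apixaban and 2/21 = 9.5% for enoxaparin; odds ratio 2.67, Fisher p = 0.31. These are authorisation requests at one institution, not trial participants without drug.

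**3. How far the handling rule moves the estimate.** Assume a mean PDC of 85% in everyone who obtains the drug, in both arms. Let a and e be the shares without drug in the apixaban and enoxaparin arms. The apixaban minus enoxaparin difference is:

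- excluded: 0.85 − 0.85 = 0
- scored 0: −0.85(a − e)
- scored by the literal formula as 1: +0.15(a − e)

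| Shares without drug (assumed) | Excluded | Scored 0 | Literal formula |
|---|---|---|---|
| 22.0% vs 9.5% (Table 2 rates, upper end) | 0 | −10.6 | +1.9 |
| 10% vs 5% | 0 | −4.25 | +0.75 |
| 5% vs 5% | 0 | 0 | 0 |

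Entries are percentage points. With equal shares the rule makes no difference to the comparison.

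**4. False non-inferiority at the margin.** Assumptions: true ITT means 85% (enoxaparin) and 70% (apixaban), with participants without drug counted as 0; share d without drug in the apixaban arm and none in the enoxaparin arm; 45 analysed per arm.

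- After exclusion the apixaban mean is 0.70/(1 − d), so the points hidden are 0.70/(1 − d) − 0.70 = 0.70d/(1 − d).
- SE = SD × √(2/45) = 0.0527 for SD 0.25 and 0.0603 for SD 0.286.
- False non-inferiority rate = P(Z > 1.645 − hidden/SE).

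| d | Points hidden | Rate, SD 0.286 | Rate, SD 0.25 |
|---|---|---|---|
| 3% | 0.70 × 0.03/0.97 = 2.2 | 10% | 11% |
| 5% | 0.70 × 0.05/0.95 = 3.7 | 15% | 17% |
| 10% | 0.70 × 0.10/0.90 = 7.8 | 36% | 43% |

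The nominal rate is 5%.

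**5. Literal scoring instead of exclusion.** Each such participant moves from 0 to 1, so the apixaban mean rises by d itself: 3, 5 or 10 points. That is more than exclusion hides at the same d.

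**The case against.** The strongest reply is that few people will be affected. The section 5.2 item removes only someone with a script for neither drug, which is usually a prescriber or system event, not poor adherence. Extended prophylaxis is standard of care whether or not the patient takes part (sections 4.2 and 5.3), allocation is at discharge, and section 8.3 switches a participant with a contraindication to the other drug and keeps the visits. This stands: loss under the section 5.2 wording is probably small. The other perioperative exclusions (no cystectomy, late discharge) mostly precede allocation and are not in question.

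Two stronger readings are tempting. A reader might infer from Table 2 that apixaban patients will more often go without drug and that the trial is therefore biased. The table counts requests, does not say what followed a denial, and is compatible with chance. A reader might also infer that section 8.2 obliges removal; its wording is permissive.

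On unfilled scripts, one can say that the endpoint is described as days on which drug was actually taken, and that staff help with the count by telephone and ask about discontinuation first. A sensible caller may well discover the unfilled script. But the only calculation the plan gives uses prescription size from the record, and it has no instruction to set that aside.

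Scoring every participant with no dispensing record as 0 would also be unsafe. The documents do not say that fills at outside pharmacies are visible, and prophylaxis withheld by a clinician is not a participant's non-adherence. Both points stand and shape the fix.

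**Conclusion.** The concern holds in this form. Sections 1.1, 5.2 and 8.2 cannot all be applied alongside the section 9.7 definition of ITT to a randomised participant who leaves without drug, and no PDC is defined for that person. For a script never filled, the section 9.3 formula as written returns a wrong primary value. This is more than missing detail.

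Direction and size are conditional. Bias toward non-inferiority follows only if more apixaban than enoxaparin participants fail to obtain the drug. The protocol anticipates this but does not show it. The 3%, 5% and 10% shares, the absence of enoxaparin loss, the 85% and 70% means and the SD range are all assumptions. Under them, exclusion hides about half of the 15-point margin at 10% (7.8 points) and about a seventh at 3% (2.2 points). A reader might multiply the excess loss by 0.85 instead; that presumes the remaining apixaban participants average 85%, which does not fit a comparison at the margin.

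**What to change.** 1. Make intent to prescribe extended prophylaxis an eligibility check completed before allocation. State that exclusion 4 and the matching item in section 8.2 do not apply once a participant is randomised, and reconcile the synopsis with sections 5.2, 8.2 and 9.7.
2. Keep every randomised participant in the ITT analysis of PDC.
3. Base the PDC numerator on the quantity actually obtained minus units remaining. Take the quantity from the pharmacy record plus a question at the POD 30 call on whether and where the prescription was filled, so that outside pharmacies are captured. A confirmed unfilled prescription then scores PDC = 0.
4. Pre-specify how randomised participants whose prophylaxis was withheld by the clinician before discharge are counted, with a sensitivity analysis. This is an estimand choice for the sponsor.

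The cost is protocol and SAP wording and one added question at an existing call; review of pharmacy records is already planned in section 7.2. The apixaban estimate may be less favourable. Because the rule can decide the primary result, it should be fixed before PDC data are analysed.

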5.3 Recruitment

The University of Pennsylvania historically performs ~70 cystectomies per year. Vanderbilt University Medical Center performs ~90 per year. To achieve the target analysis group of 90 patients we plan to enroll 108 (see section 9.3.1). Thus the planned recruitment/enrollment period is approximately 12 months.

Recruitment will take place in outpatient offices. We will review the medical charts of patients seeing our Urologic oncology surgeons a week ahead of time and flag charts that suggest a radical cystectomy may be an indicated therapy for a patient. Staff will plan to be available on these days to screen and enroll as able.

The treating physician will discuss post-operative extended prophylaxis (EP) with anticoagulants with the patient during their visit because it is standard of care. Within this context the treating physician will introduce the option to participate in the trial and undergo randomization between forms of EP, however it will be made clear to the potential participant that they will receive standard of care EP regardless of their choice to participate or not.

After the visit, further discussion of the trial and screening will be performed by trial staff other than the treating physician, and participants will be allowed to think about their decision after the initial discussion and enroll at a later date (as long as they enroll prior to undergoing surgery). Both of these features will help further mitigate any undue pressure patients may feel. If a patient cannot be approached in person or decides they would like to think longer about their decision to participate, a member of the research team will contact them by phone and complete the remaining enrollment process over the phone and electronically.

6 STUDY INTERVENTION

Both enoxaparin and apixaban are FDA approved in the setting of VTE prophylaxis and considered standard of care for EP after radical cystectomy. Study personnel will not be directly providing or administering either drug. Rather, the study intervention is the randomization to receive a prescription (with standard clinical counseling) for either of the two forms of prophylaxis. The participant will then be responsible for filling the prescription at their own cost and self-administering the anticoagulant, as would be standard of care after a radical cystectomy. The anticoagulants will be prescribed according to the clinical standard of care: 40 mg injected subcutaneously once daily for enoxaparin and 2.5 mg tablet taken orally twice daily for apixaban. Doses may be reduced in increased based on the patient's medical comorbidity profile (for example weight and CrCl) according to standard prescribing practices. Regardless of the time of day of discharge, participants will be instructed to start self-administering the medication the day after discharge, and continue through post-op day 30.

Participants who fail to receive a prescription for either anticoagulant will be considered not to have received the study intervention. Participants who receive the prescription but report poor compliance with the prescription have still received the study intervention; their poor compliance is tracked as the primary outcome of the study.

7 STUDY ASSESSMENTS

At the time of enrollment, participants will be offered to complete the Demographics questionnaire either in person (if applicable), via phone (if applicable), or via a secure REDCap link emailed to them.

Participants will be contacted via phone on POD30 and POD90. During the phone call, participants will be given the option to receive an email with a secure link to REDCap to complete the majority of the study visit electronically (PMAS, Patient Satisfaction, and COST

questionnaires). Medication counting and screening for adverse events including VTE and bleeding must be done over the phone rather than via emailed link.

Study assessments will be conducted by staff other than the treating physician, and staff members will clearly state the contact is part of the research study, not part of routine clinical care.

